6.3 Screen Failures and Retesting/Rescreening

Subjects who fail to qualify for the study based on laboratory tests may be considered for rescreening at the discretion of the Investigator if it is considered that the subject's status has

changed, and the subject may now qualify for the study. Screening is limited to 3 attempts (initial Screening and 2 additional rescreening attempts). A new informed consent is required to be signed prior to every rescreening. Rescreened subjects should be assigned a new subject number.

Subjects who initially fail to qualify for the study based on laboratory test results may be retested once for each laboratory parameter within the 8-week Screening Period, per Investigator discretion.

7.0 STUDY INTERVENTION

7.1 Study Intervention(s) Administration

7.1.1 Study Intervention Description

A multi-center, randomized, open-label, active-controlled study of the efficacy and safety of conversion from long-acting ESA (Mircera) to vadadustat TIW for the maintenance treatment of anemia in hemodialysis patients. Following a Screening period of up to 8 weeks (56 days), subjects who meet all inclusion and none of the exclusion criteria, Mircera will be discontinued and subjects will be randomized 1:1:1 to vadadustat 600 mg TIW, vadadustat 900 mg TIW, or to remain on Mircera according to the dialysis center's protocol.

Randomization will be stratified by dialysis organization:

The minimum dose of vadadustat will be 300 mg TIW and the maximum dose will be 1200 mg TIW.

Following randomization, there will be 2 periods during the study:

- Conversion and Maintenance Period (Weeks 0 to 52): conversion to vadadustat TIW or to remain on Mircera (Weeks 0 to 20). There will be a primary efficacy evaluation period (Weeks 20 to 26) and a secondary efficacy evaluation period (Weeks 46 to 52).
- Safety Follow-up Period (ET and Follow-Up): post-treatment safety follow up visit (ET/EOT +4 weeks) either in person or via telephone.

7.1.2 Dosing and Administration

The aim is to achieve and maintain Hb levels within the target range of 10.0 to 11.0 g/dL inclusive, while targeting the middle of the range and minimizing excursions outside the target range.

Dosing will be initiated at Baseline and the first dose of vadadustat will be administered at the hemodialysis unit after other Baseline procedures have been completed. Thereafter, vadadustat is anticipated to be administered at the hemodialysis unit. Subjects may take vadadustat with or without food and will be instructed to swallow the tablet(s) whole. Subjects are to take vadadustat at roughly the same time each day.

Mircera will be administered IV at the hemodialysis unit based on according to the dialysis center's protocol.

Note: For all subjects, it is recommended that no additional ESA doses will be administered after SV2 after the subject has met all eligibility criteria and before Baseline. For all subjects, it is required that a minimum of 14 days be observed between the last dose of Mircera and the

Baseline visit. If an ESA other than Mircera was administered during the Screening period, the subject will be a screen failure.

After discussion with the Medical Monitor, screening may be extended for an additional 2 to 4 weeks based on subject's Hb level or Hb trajectory or based on timing of last Mircera dose given during Screening and the Baseline visit.

For subjects who are randomized to the Mircera treatment arm, the initial dosing regimen in the study (starting from Baseline) will be according to the dialysis center's protocol. The timing of randomization should align with next anticipated dose of Mircera.

Study Drug Guidelines for Dose Adjustment

Dose adjustments will be guided by central laboratory Hb concentrations throughout the study to determine if vadadustat or Mircera doses will be adjusted, interrupted, or maintained. Mircera dosing will be based on standard of care laboratory measures according to the dialysis center's protocol.

Guidelines for vadadustat dose adjustment are as follows (see [Appendix 1](#)):

- Dose adjustments are based on the Investigator's clinical discretion, incorporating the protocol guidance below as well as the subject's current Hb level, trajectory, and variability; symptoms; CV risk; and other features of his/her clinical condition(s).
- If a dose increase or decrease is required to achieve and maintain Hb levels within the target range of 10.0 to 11.0 g/dL inclusive, dose is adjusted by 1 dose level (vadadustat 300 mg).
- A one-time dose increase after the first 2 weeks of dosing after randomization is allowed. Thereafter, in general, do not increase the dose more frequently than once every 4 weeks.
 - A subject's dose may be increased by 1 dose level (300 mg TIW) if the subject has a decline in Hb ≥ 0.5 g/dL from Baseline in the first 2-week period (the initial period from Baseline to Week 2 following conversion from Mircera) and if Hb is < 10.0 g/dL.
- Reduce the dose in the setting of a rapid rise in Hb (defined as > 1.0 g/dL in any 2-week period or > 2.0 g/dL in any 4-week period).
- Reduce the dose in the setting of Hb > 11.0 g/dL.
- Interrupt the dose in the setting of a Hb > 12.0 g/dL until Hb value falls below 11.0 g/dL. After Hb falls below 11.0 g/dL, restart study drug at a lower dose.

The minimum dose of vadadustat will be 300 mg TIW (1 tablet TIW) and the maximum dose will be 1200 mg TIW. Subjects whose dose of vadadustat is interrupted due to elevated Hb will continue in the study. Unless contraindicated, treatment will be resumed whenever possible and assessed at every visit following study drug interruption.

Mircera will be administered as standard of care. Dose adjustments will be made according to the dialysis center's protocol.

7.1.3 Study Medication Stopping Rules for Liver Function Test Changes

Vadadustat must be permanently discontinued if a subject meets 1 of the following criteria:

- ALT or AST $> 3 \times$ ULN and total bilirubin $> 2 \times$ ULN

- ALT or AST >3x ULN and international normalized ratio (INR) >1.5
- ALT or AST >8x ULN
- ALT or AST remains >5x ULN over 2 weeks (re-challenge generally should be avoided with ALT or AST >5x ULN unless there are no other good therapeutic options)
- ALT or AST >3x ULN with symptoms (e.g., fatigue, nausea, vomiting, right upper quadrant pain, fever, rash) or eosinophilia

See [Section 9.11](#) for reporting requirements related to a subject being permanently discontinued based on meeting the laboratory abnormalities listed above.

7.2 Preparation/Handling/Storage/Accountability

7.2.1 Acquisition and Accountability

Vadadustat for oral administration will be provided and shipped by the Sponsor.

The investigator or designated study personnel will be responsible for preparing vadadustat for dispensing to the subject and for vadadustat supply accountability.

Mircera will be supplied by the dialysis unit which will be also responsible for mircera supply accountability.

Refer to the Pharmacy Manual for additional details.

7.2.2 Formulation, Appearance, Packaging and Labeling

Vadadustat will be provided as 300 mg oval, yellow tablets debossed with “VDT” on 1 side and “300” on the other side for oral administration. The tablets will be packaged in high-density polyethylene bottles with child-resistant closures, polypropylene liner, and induction seal. Labeling will be in accordance with current Good Manufacturing Practices (GMP) and local regulatory requirements.

7.2.3 Product Storage and Stability

Vadadustat should be stored per the investigational labels. Please consult the Pharmacy Manual for details on storage and managing temperature excursions.

7.2.4 Preparation

Not applicable.

7.3 Measures to Minimize Bias: Randomization and Blinding

Subjects will be randomized 1:1:1 to vadadustat 600 mg TIW, vadadustat 900 mg TIW, or to remain on Mircera.

Randomization will be stratified by dialysis organization:

This will be an open-label study. Treatment assignment will be done through a validated electronic system. The Investigator, Sponsor, and contract research organization (CRO) study teams will not be aware of which treatment will be assigned next. Treatments will be

administered in an open-label fashion. The sponsor and CRO study teams will be blinded to ‘by treatment’ aggregated analyses except for the unblinded statistician.

7.4 Study Intervention Compliance

Subjects will take the dose of study drug on dialysis days. If a dose is forgotten, the missed dose will not be replaced.

Subjects will be questioned on whether they have experienced any problems related to the dosing of study medication.

7.5 Concomitant Therapy

7.5.1 Erythropoiesis-stimulating Agents

Co-administration of any ESA with vadadustat is prohibited. In the setting of ESA rescue therapy, the initial dose of ESA rescue therapy may be administered on the same day as the last vadadustat dose prior to vadadustat dose interruption ([Section 7.5.5.2](#)) if deemed medically necessary at the discretion of the Investigator. Guidelines for ESA administration as rescue therapy are provided in Section 7.5.5.2. All efforts will be made to avoid inadvertent administration of ESAs resulting from adherence to ESA hemodialysis center protocols (e.g., ESA protocols for patients on hemodialysis). If ESA is inadvertently administered to subjects actively receiving vadadustat treatment, vadadustat treatment will be stopped and the event will be reported as a protocol deviation.

For all subjects, it is required that a minimum period as outlined below be observed between the last dose of ESA administered during Screening and Randomization visit:

- 2 days after last dose of epoetin alpha.
- 7 days after last dose of darbepoetin alfa.
- 14 days after last dose of methoxy polyethylene glycol-epoetin beta (Mircera).

7.5.2 Iron Supplementation and Phosphate Binders

Investigators will prescribe iron supplementation (IV, oral or intradialytic) as needed throughout the study to maintain ferritin and TSAT according to the Schedule of Activities (SoA) ([Section 1.3](#)). The use of iron-based phosphate binders (e.g., ferric citrate) is permitted.

Important: Subjects already receiving oral iron supplementation as part of their treatment plan may continue their current treatment regimen. Because of the potential for oral iron and phosphate binders to reduce the bioavailability of vadadustat, the trial medication is not to be administered concurrently with an oral iron supplement (including multivitamins containing iron), iron-containing phosphate binders, non-iron-containing phosphate binders, or any oral medications containing iron.

Subjects will be instructed to take any non-iron-containing phosphate binders with a meal at least 2 hours before or 1 hour after the dose of vadadustat. Subjects will be instructed to take iron-containing supplements and phosphate binders at least 1 hour after the dose of vadadustat.

Investigators will prescribe IV iron as needed with dosing according to the dialysis center’s protocol. Iron supplementation details will be captured in the appropriate electronic case report form (eCRF).

7.5.3 OATP1B1/1B3 Substrates (eg, Statins)

Investigators should adjust the dose of these concomitant medication as follows:

- Simvastatin, maximum daily dose of 20 mg.
- Rosuvastatin, maximum daily dose of 10 mg.

7.5.4 Sulfasalazine, Other Breast Cancer Resistance Protein Substrates, and Probenecid

Exposures to sulfasalazine (moderately) and mesalamine (mildly) were increased with co-administration of vadarustat based on a study in healthy adults. In subjects taking vadarustat, sulfasalazine and other clinically relevant substrates of the breast cancer resistance protein (BCRP) transporter (e.g., sulfasalazine, methotrexate, mitoxantrone, imatinib, irinotecan, lapatinib, topotecan, tenofovir, glecaprevir, pibrentasir, or sofosbuvir), caution should be taken during the study.

Probenecid, an inhibitor of UDP-glucuronosyltransferase (UGT) and the organic anion transporter (OAT)1/3 transporters, increased vadarustat area under the curve and is prohibited during the study

7.5.5 Rescue Medicine

To ensure the safety of subjects and to standardize the use of rescue in the study, rescue therapy guidelines are provided.

7.5.5.1 Red Blood Cell Transfusion

Investigators will use their local institution's transfusion guidelines when determining whether to transfuse a study subject. In general, in the event of an acute or severe loss of blood, a RBC transfusion will be administered as clinically indicated. In less severe instances but where there may be worsening of anemia or moderate to severe symptoms of anemia, RBC transfusions are permitted at the discretion of the Investigator given medical necessity. Study drug may be continued during the transfusion period.

Reasons for RBC transfusion will be captured in the appropriate eCRF.

7.5.5.2 Erythropoiesis-stimulating Agent Use

ESA Rescue administration will be allowed when medically necessary at the discretion of the Investigator or if a subject is hospitalized. In the setting of ESA rescue therapy, the initial dose of ESA rescue therapy may be administered on the same day as the last vadarustat dose prior to vadarustat dose interruption if deemed medically necessary at the discretion of the investigator. In general, ESA rescue will be allowed in subjects with Hb <9.0 g/dL, and ESA rescue will be stopped when Hb ≥9.5 g/dL. ESA therapy will be administered using an approved ESA and dosing as per the local institution's guidelines and per the approved product label.

While receiving ESA therapy, subjects randomized to vadarustat must temporarily interrupt vadarustat. A minimum interval will be observed prior to restarting vadarustat after the last dose of ESA, and treatment will be resumed after the following minimum intervals:

- 2 days after last dose of epoetin alfa

- 7 days after last dose of darbepoetin alfa
- 14 days after last dose of methoxy polyethylene glycol-epoetin beta (Mircera)

Following ESA administration, vadadustat will be resumed at the same dose as previously used or one dose higher and adjusted according to the dose adjustment algorithms ([Section 7.1.2](#) and [Appendix 1](#)) at the discretion of the Investigator.

Reasons for ESA Rescue use will be captured in the appropriate eCRF.

8.0 DISCONTINUATION OF STUDY INTERVENTION AND SUBJECT DISCONTINUATION/WITHDRAWAL

8.1 Discontinuation of Study Intervention

8.1.1 Temporary Interruption of Study Drug

During the study, a subject may interrupt vadadustat for any of the following reasons:

- AE
- Missed hemodialysis visit
- Investigator's discretion
- Rapid rise in Hb (defined in Section 7.1.2)
- Hb above 11.0 g/dL
- ESA use

Unless contraindicated, treatment will be resumed whenever possible and assessed at every visit following study drug interruption.

8.1.2 Permanent Discontinuation of Study Medication

Subjects who permanently discontinue study medication prior to study completion will not continue in the study. These subjects are to have their ET visit at the time of permanently discontinuing study medication and perform a 4-week safety follow-up after ET visit.

Subjects may permanently discontinue study medication for any of the following reasons:

- AE
- Investigator's discretion
- Subject withdrawal of consent
- Lack of efficacy
- Lost to follow up despite reasonable efforts by the Investigator to locate the subject
- Death
- Other reasons (pregnancy, kidney transplantation, specific reasons to be documented by the Investigator)

Lack of efficacy is defined as an inadequate response to vadadustat in the Investigator's opinion.

Subjects who undergo a solid organ (including kidney), hematopoietic stem cell, or bone marrow transplantation will have vadadustat permanently discontinued.

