There were 266 (15.0%) and 276 (15.6%) subjects that experienced TEAEs resulting in death in the vadadustat and darbepoetin alfa treatment groups, respectively. The most frequent TEAEs by PT resulting in death were similar between both treatment groups, and included cardiac arrest (2.0% and 2.1%), septic shock (1.3% and 1.2%), and cardio-respiratory arrest (1.2% and 1.3%) for the vadadustat and darbepoetin alfa treatment groups, respectively.

In the vadadustat treatment group, all deaths due to TEAEs were considered unrelated. In the darbepoetin alfa treatment group, only 1 death due to TEAE of acute MI was considered related. The TEAEs that resulted in death were similar across both treatment groups.

In addition to Study CI-6548-0017, Study CI-6548-0025, a Phase 2, randomized, open-label study to evaluate vadadustat for the treatment of anemia in hemodialysis subjects converting from epoetin alfa therapy, has recently completed the active patient phase but summary efficacy and data are not available at this time. Subjects who were randomized to vadadustat were treated QD from Day 1 to Week 12 and if Week 12 criteria were met, then vadadustat was administered TIW from Weeks 12 to 20. Dose levels of vadadustat administered in this study include

150, 300, 450, 600, 750 and 900 mg QD or TIW. One hundred twenty-nine subjects were randomized to vadadustat and 36 subjects were randomized to epoetin. All randomized subjects received at least one dose of study drug. Of the randomized subjects, 60.5% of subjects in the vadadustat group and 88.9% of subjects in the epoetin group completed treatment and 76.7% of subjects in the vadadustat group and 94.4% of subjects in the epoetin group completed the study.

Overall, taking into account the entire vadadustat clinical development program, the safety profile to date supports the ongoing clinical development of vadadustat as an orally bioavailable agent for the treatment of anemia associated with CKD.

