Transplantation – During this long-term study, it is anticipated that some subjects may receive a kidney transplant. These events will not be recorded as AEs. Subjects will discontinue study medication for receipt of a kidney, other solid organ, hematopoietic stem cell or bone marrow transplant and should continue with the SoA and safety assessments as described in [Section 8.1.2](#).

Malignancy – During this long-term study, some subjects may develop a newly diagnosed malignancy or a recurrence of a malignancy. At the discretion of the Investigator, these subjects may continue study medication. For reporting of AEs of malignancy, see [Section 9.11.1.2](#).

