6.11.1 Primary Estimand

The primary estimand defining the treatment effect of interest in this trial uses the treatment policy strategy specified in the [ICH E9 \(R1\) Addendum \[FDA 2021\]](#). In this trial, the research question is to compare the assignment of Mircera to vadadustat, regardless of intercurrent events. The primary analysis will be performed in the randomized population in accordance with intent-to-treat. This means the analysis will include individuals who never received treatment, discontinued treatment, were rescued with any therapy, and withdrew consent. The estimate of the treatment effect of interest will be the one regardless of whether the intercurrent event occurred.

The primary estimand for this trial is defined by the following components:

- Treatment: vadadustat with rescue therapy as needed versus Mircera with rescue therapy as needed
- Population: randomized population.
- Variable: change in Hb from Baseline (average pretreatment Hb) to the primary evaluation period (average Hb from Weeks 20 to 26, inclusive).
- Intercurrent event: never received treatment, discontinued treatment, rescued with any therapy or withdrew consent.
- Population-level summary: difference in mean change in Hb from baseline to the primary evaluation period between the vadadustat groups and Mircera control group.

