6.11.2 Primary Efficacy Analyses

The primary efficacy endpoint is defined as the mean change in Hb between Baseline (average pretreatment Hb) and the primary evaluation period (average Hb from Weeks 20 to 26, inclusive).

The primary analysis of the primary endpoint will use the randomized population with imputation of data. All intercurrent events will be handled by treatment policy strategy ([Section 6.11.1](#)). Unobserved data after intercurrent events, including Hb outcomes and any covariates to be used in the models, will be imputed with the randomized treatment group to which the subject was randomized using multiple imputation under fully conditional specification (FSC) method as described in [Appendix B](#). Data up to

scheduled visit of week 26 will be included in the primary efficacy analyses. Analysis of covariance (ANCOVA) as described in [Appendix A](#) will be used to calculate the LS mean (SE) by treatment group and LS mean difference (SE), 95% confidence intervals (CI) of the difference in mean change in Hb from baseline to the primary evaluation period between the vadadustat groups and Mircera control group, with the randomization stratification factor (Dialysis organization) and Baseline Hb as covariates.

Treatment comparisons will be performed between the vadadustat and Mircera groups. Subjects in the vadadustat starting dose groups of 600 mg or 900 mg TIW will have their doses adjusted to maintain Hb levels of 10.0 to 11.0 g/dL following the protocol's dosing algorithm.

- Noninferiority of vadadustat will be established if the lower limit of 2-sided CI is greater or equal to -0.75 g/dL for combined vadadustat dosing groups minus Mircera.

If the lower limit of the 2-sided 95% confidence interval for the difference between the mean Hb change from baseline to Weeks 20 to 26 in the vadadustat group and the mean Hb change from baseline in the Mircera group is above zero, superiority will have been established and the finding will be interpreted as providing evidence of a greater change from baseline in Hb for vadadustat relative to the control arm. Because the same 95% confidence interval is used to the superiority test, no adjust of multiplicity is needed.

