6.11.3 Secondary Efficacy Analyses

The study has one secondary efficacy endpoint which will be analyzed formally only if the primary analysis meets the noninferiority margin.

Mean change in Hb between Baseline (average pretreatment Hb) and the secondary evaluation period (average Hb from Weeks 46 to 52, inclusive) will be analyzed using the same methodology as specified for the primary efficacy endpoint. Evaluation of the average change in Hb will employ the approach described for the primary endpoint assessing Weeks 46 to 52 instead of Weeks 20 to 26.

Sensitivity analyses analogous to those performed for the primary efficacy endpoint will be repeated to assess mean change in Hb from Baseline to Weeks 46 to 52. For ANCOVA models, the analysis period of Weeks 46 to 52 will replace the analysis period of Weeks 20 to 26, and for MMRM, the models will be extended to include analysis period up to week 52. The analysis will be repeated for the vadadustat 900 mg TIW starting dose group vs. Mircera and vadadustat 600 mg starting dose group vs. Mircera as exploratory analyses.

After the non-inferiority for both primary and key secondary endpoints have been established, If the lower limit of the 2-sided 95% confidence interval for the difference between the mean Hb change from baseline to Weeks 20 to 26 in the vadadustat group and the mean Hb change from baseline in the Mircera group is above zero, superiority will have been established and the finding will be interpreted as providing evidence of a greater change from baseline in Hb for vadadustat relative to the control arm. Because the same 95% confidence interval is used to the superiority test, no adjustment for multiplicity is needed.

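### The SAP claims treatment policy for discontinued treatment, but the protocol ends participation at permanent discontinuation, so early stoppers' primary outcome is imputed roughly as if they had stayed in the study

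*Protocol*

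**What the plan says.** **Estimand.** SAP 6.11.1 adopts treatment policy and lists the events covered: "Intercurrent event: never received treatment, discontinued treatment, rescued with any therapy or withdrew consent". SAP 6.11.2 repeats: "All intercurrent events will be handled by treatment policy strategy".

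**Follow-up.** Protocol 8.1.2: "Subjects who permanently discontinue study medication prior to study completion will not continue in the study". Footnote b of the Schedule of Activities (Protocol 1.3) says the same. Such subjects have an early termination visit when they stop and a safety contact 4 weeks later. Protocol 5.1 allows that contact by phone. SAP 6.2, Table 1, assigns only vital signs, dialysis access type and phlebotomy to it, not Hb.

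**Missing outcomes.** Under SAP 6.11.2, Hb not observed after an intercurrent event "will be imputed with the randomized treatment group to which the subject was randomized using multiple imputation under fully conditional specification (FSC) method". SAP Appendix B.3 states that the primary imputation model assumes MAR in both arms.

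**Claims.** Noninferiority needs a lower 95% confidence limit of at least -0.75 g/dL for combined vadadustat minus Mircera. If that limit is above zero, SAP 6.11.2 says "superiority will have been established and the finding will be interpreted as providing evidence of a greater change from baseline in Hb for vadadustat". SAP 6.11.3 places a superiority statement later: "After the non-inferiority for both primary and key secondary endpoints have been established".

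**The concern.** Treatment policy for discontinuation asks what Hb was in Weeks 20 to 26 whether or not the subject was still on drug. Answering that needs Hb from subjects who have stopped, and the protocol stops collecting it. Window data therefore come almost wholly from subjects still in the study on their assigned treatment, including those rescued or temporarily interrupted. Imputing early stoppers from those subjects gives them the Hb expected had they stayed.

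What is at stake is mainly the description of the primary result, and of any superiority claim, as an effect regardless of discontinuation. The planned sensitivity analysis that sets Hb after the end-of-treatment visit to missing (SAP 6.11.2.1) adds almost nothing for early stoppers, because Protocol 8.1.2 has already made those values missing.

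**Working it through.** **1. The plan's own figure.** Inputs from Protocol 10.2 and SAP 3.3: SD 1.2, margin 0.75, true difference 0, 150 per arm, 30% dropout. Evaluable per arm: 150 × 0.70 = 105.
- Pairwise: SE = 1.2 × √(2/105) = 0.1656; power = Φ(0.75/0.1656 − 1.96) = 99.5%.
- Combined 2:1: SE = 1.2 × √(1/210 + 1/105) = 0.1434; power = Φ(0.75/0.1434 − 1.96) = 99.95%.

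Both agree with the stated power above 90%. The sample size is not in question.

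**2. Which subjects are affected.** SAP Table 1 runs the primary window from Day 127 to Day 196. A stop before Day 127 puts the early termination Hb outside it. A stop inside the window can contribute an Hb, and an unscheduled Hb is mapped by study day. The point therefore concerns permanent stops before Day 127.

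**3. Size of the gap.** Let p be the share of an arm stopping before Day 127, and d the mean off-drug Hb of those subjects minus the mean imputed for them under MAR. The other 1 − p contribute equally to both quantities, so each arm differs by p × d:

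gap (treatment-policy difference minus MAR estimate) = pV × dV − pM × dM

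The documents give neither p nor d. Assume equal p, dM = 0 and dV = ±0.5 g/dL. The 30% row puts all planned dropout before Day 127.

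| p, both arms | gap, dV = −0.5 | gap, dV = +0.5 |
|---|---|---|
| 10% | −0.05 | +0.05 |
| 20% | −0.10 | +0.10 |
| 30% | −0.15 | +0.15 |

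With equal p and equal d in both arms the gap is 0.

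**4. Does MAR imputation recover the hypothetical effect?** A large-sample simulation let stopping depend on early Hb change, observed no off-drug Hb and used within-arm regression imputation. With assumed stopping of 39.5% and 11.1% and an off-drug shift of −0.5 g/dL in both arms, the MAR estimate was 0.00, the had-they-stayed effect 0.00 and the treatment-policy effect −0.14 g/dL.

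**5. Noninferiority at a true difference of 0.** With 300 versus 150 randomized and only observed subjects counted, SE = 1.2 × √(1/(300(1−p)) + 1/(150(1−p))) = 0.1265, 0.1342 and 0.1434 for p = 10%, 20% and 30%. P(noninferiority) = Φ((0.75 − gap)/SE − 1.96). The lowest value in the table's cases is Φ((0.75 − 0.15)/0.1434 − 1.96) = 98.7%.

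**6. What the tipping point shows.** Appendix B.3 lowers imputed vadadustat Hb in steps of 0.1 until the lower limit falls below −0.75. Take an assumed MAR estimate of +0.30 with p = 20%, and hold the interval width fixed:
- lower limit = 0.30 − 1.96 × 0.1342 = 0.037, so superiority would be declared;
- shift to reach 0 = −0.037/0.20 = −0.19 g/dL;
- shift to reach −0.75 = −(0.037 + 0.75)/0.20 = −3.94 g/dL.

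The loop passes through the first crossing but reports only the second.

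**The case against.** The strongest reply is that the strategy for intercurrent events and the handling of missing data are separate matters. SAP 6.11.2 says openly that unobserved data will be imputed, and any Hb that does exist in the window is kept. On that reading this is a treatment-policy estimand resting on a strong MAR assumption, which the tipping point stress-tests. This stands for rescue and temporary interruption, where follow-up continues. It does not stand for permanent discontinuation before Day 127: there the protocol's own rule, not chance loss, removes the data, and no readable step draws on off-drug subjects.

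Redaction is a fair limit. The imputation code and predictors are hidden, so an off-drug imputation step cannot be ruled out. The conclusion rests on the readable randomized-arm and MAR statements and says nothing about how death or transplant is handled.

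It is also true that relabelling leaves the estimate, interval and decision rule unchanged, and that the zero-crossing shift is already computed. The label still governs what the result may be said to show, and reporting that shift still matters if superiority is claimed.

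For transplant, Protocol 9.11.1.1 says subjects "should continue with the SoA and safety assessments as described in" Section 8.1.2. A reader might infer a direct contradiction with 8.1.2. Because the sentence defers to 8.1.2, this is loose wording and only a minor point to reconcile.

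**Conclusion.** The mismatch holds. For subjects who permanently stop before Day 127, the data collection cannot deliver the declared treatment-policy estimand, and on the readable text the analysis approximates a hypothetical strategy for them. The gap of 0.05 to 0.15 g/dL in either direction is an illustration under assumed shifts and stopping shares. The documents fix neither its size nor its sign.

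Two stronger readings are not supported:

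- **False-claim risk.** A reader might infer a raised chance of a false claim at the null (noninferiority at a true −0.75, or superiority at a true 0). The formula Φ(−gap/SE − 1.96) gives 6%, 11% and 18% for dV = −0.5 at p = 10%, 20% and 30%, against a nominal 2.5%. It also gives 0.9%, 0.3% and 0.1% for dV = +0.5. No passage supports either shift. For noninferiority with dV = −0.5, also requiring the result to survive a tipping-point shift of that size returns the rate to 2.5%.
- **Unequal stopping.** An earlier conversion study reported that "60.5% of subjects in the vadadustat group and 88.9% of subjects in the epoetin group completed treatment" (Protocol 3.4). A reader might take the implied 39.5% and 11.1% as this trial's early stopping shares. That study used epoetin as comparator and daily dosing to Week 12, with criteria for moving to three times weekly. Some of its stops may have come after Day 127, and 39.5% exceeds this plan's 30% dropout. It shows only that stopping may differ between arms.

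Noninferiority at a true difference of 0 is not at risk. The remaining exposure is the estimand label and the robustness shown for a superiority claim.

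**What to change.** **Main change, SAP 6.11.1 and 6.11.2:**
- keep treatment policy for rescue, and say that it also covers temporary interruption;
- state a hypothetical strategy for permanent discontinuation;
- treat withdrawn consent as missing data rather than as an event under treatment policy;
- word the primary conclusion to match;
- if superiority is claimed, report the tipping-point shift at which the lower limit reaches 0, alongside the shift at which it reaches −0.75.

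This costs SAP wording and one reported number, with no extra run. The downside is that the primary result can no longer be called treatment policy for discontinuation.

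**Alternative, if still feasible:** collect Hb in Weeks 20 to 26 and 46 to 52 after drug is stopped, and use it in the primary analysis. This needs a protocol amendment and could move the estimate either way, but it would support the declared strategy for subjects with those values.

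**Minor:** reconcile the transplant wording in Protocol 9.11.1.1 with 8.1.2.
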